Twenty-five pregnancies occurring between 2012-2017 in 22 patients seen at Mount Sinai Hospital and Mayo Clinic have been retrospectively reviewed (see figures). Pump settings at the initial visit and at designated 2-week intervals each trimester were analyzed. Compared to the initial visit, basal infusion rates overnight and in the morning decreased during the 1st trimester and rose in the 2nd and 3rd trimesters. Midday and evening infusion rates peaked during the late 2nd trimester to early 3rd trimester before plateauing during the last month of pregnancy. Carbohydrate ratios became more aggressive after week 12 with the earliest change in settings seen at breakfast. By the end of pregnancy, carbohydrate ratios had decreased by an average of 45%. Insulin sensitivity factors became more aggressive starting in the late 2nd trimester resulting in a 20% change from baseline by the end of pregnancy [5].

Summary: Understanding the hormonal and metabolic complexity as well as the subsequent requirements of adaptive insulin management over the entire gestation period in T1D will enable us to develop mathematical models that will describe the fluctuating glucose-insulin interactions during pregnancy. A multicenter database including CGM and insulin settings/bolus information from pregnant women during the gestation period will be collected to: 1) to serve as a comparator group for analysis of future AP studies data, 2) to further examine the glycemic variability and insulin management requirements throughout pregnancy to refine our AP algorithms, 3) to provide additional information on CGM use in pregnant women in comparison to fingerstick data utility, patient acceptance, and pregnancy outcomes.

Study Design and Methods

Methods: *Describe, in detail, the research activities that will be conducted under this protocol:*

All pregnant women with T1D at up to five sites on insulin pumps (CSII/SAP/PLGS) will be offered enrollment in a prospective study that will capture: 1) Dexcom G6 CGM data, 2) self-monitoring of blood glucose (SMBG), 3) insulin pump settings, 4) insulin delivery records, and 5) maternal and fetal outcomes.

Outpatient Screening and Enrollment:

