Postpartum visit: After delivery, the participants will return study devices at or around the time of their routine post-partum follow up visit. Medical records including method of delivery, gestational age at delivery, neonatal intensive care unit (NICU) admissions, neonatal hypoglycemia, fetal weight, and length of hospital stay will be reviewed. The infant's medical record will also be accessed to retrieve post-delivery medical information. Subjects will also be asked if they were given any medications such as steroids that are known to cause insulin resistance which would impact blood glucose control. Subjects will be asked to complete the CGM-SAT survey (a survey assessing satisfaction with the glucose sensor) at this visit[12].

Data analysis:

Data from the 3 sites will be de-identified and collected in a central HIPPA compliant data repository.

Patterns of insulin and glucose control (including time in range 60-140 mg/dL, frequency of severe hypoglycemic events, time spent above target range, time spent in hypoglycemic range, episodes of clinically significant hyperglycemia with CGM >180 mg/dL, episodes of ketoacidosis requiring emergency room or hospital admission) will be analyzed and association with outcomes calculated.

Maternal and fetal outcomes include gestational age at delivery, birthweight of baby, fetal malformations, incidence of macrosomia [13], preterm birth, neonatal hypoglycemia (requiring IV dextrose), neonatal NICU stay, method of delivery, adverse events associated with delivery including shoulder dystocia, and maternal complications including preeclampsia and polyhydramnios.

CGM data will be compared to time-matched SMBG data in the pregnant population.

[name] from Mayo Clinic Rochester is the Program Statistician and will be involved in the analyses.

Resources: *Describe the available resources to conduct the research (personnel, time, facilities, mentor commitment, etc.):*

— (1a) This is a multisite study involving Mayo Clinic and non Mayo Clinic sites. *When checked, describe in detail the research procedures or activities that will be conducted by Mayo Clinic study staff.*

Mayo Clinic staff will perform the activities described above for 10 participants. The other sites will conduct the same activities on their participants. Mayo Clinic staff will also collect de-identified data from all sites for analysis.

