— (1b) Mayo Clinic study staff will be engaged in research activity at a non Mayo Clinic site. *When checked, provide a detailed description of the activity that will be conducted by Mayo Clinic study staff.*

Subject Information

Target accrual is the proposed total number of subjects to be included in this study at Mayo Clinic. A "Subject" may include medical records, images, or specimens generated at Mayo Clinic and/or received from external sources.

Target accrual: 300 subjects across 3-5 sites. We plan to enroll 60 patients each at Mount Sinai New York, Mayo Clinic Rochester, Sansum Diabetes Research Center, Santa Barbara, CA. In addition, we hope to extend the study to sites such as the Barbara Davis Center, Denver, Colorado and Joslin Clinic, Boston, MA.

Subject population (children, adults, groups): Pregnant women 18 years of age or older with T1D

Inclusion Criteria:

- Clinical diagnosis, based on investigator assessment, of T1D for at least one year and using insulin for at least 1 year.
- Criteria for documented hyperglycemia (at least 1 must be met):
 - Fasting glucose ≥ 126 mg/dL
 - Two-hour OGTT glucose ≥ 200 mg/dL
 - HbA1c $\geq 6.5\%$ documented
 - Random glucose ≥ 200 mg/dL with symptoms

- No data at diagnosis is available but the participant has a convincing history of hyperglycemia consistent with T1D
- Criteria for requiring insulin at diagnosis (1 must be met):
 - Participant required insulin at diagnosis and continually thereafter.
 - Participant did not start insulin at diagnosis but upon investigator review likely needed insulin (significant hyperglycemia that did not respond to oral agents) and did require insulin eventually and used continually.
 - Participant did not start insulin at diagnosis but continued to be hyperglycemic, had positive islet cell antibodies – consistent with latent autoimmune diabetes in adults (LADA) and did require insulin eventually and used continually.
- Currently using an insulin pump for diabetes management
- Currently using or willing to use an insulin-to-carbohydrate ratio to calculate meal bolus sizes
- Willing to change insulin infusion site at least every 3 days.
- Confirmed pregnancy
- Current gestational age ≤16 weeks
- Age 18-40 years
- HbA1c <10.0%
- Demonstration of proper mental status and cognition for the study
- Ability to access the internet and upload CGM data remotely if needed
- An understanding of and willingness to follow the protocol and sign the informed consent

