Dates: All elements of dates [month, day, and year] directly related to an individual, their birth date, date of death, date of diagnosis, etc. Note: Recording a year only is not a unique identifier.	X	
Social Security number		
Medical device identifiers and serial numbers	X	X
Biometric identifiers, including finger and voice prints, full face photographic images and any comparable images		
Web Universal Resource Locators (URLs), Internet Protocol (IP) address numbers, email address		
Street address, city, county, precinct, zip code, and their equivalent geocodes	X	
Phone or fax numbers	X	
Account, member, certificate or professional license numbers, health beneficiary numbers		

Vehicle identifiers and serial numbers, including license plate numbers		
Check 'None' when none of the identifiers listed above will be recorded, maintained, or shared during the conduct of this study. (exempt category 4)	 None	 None

Data Analysis

Power analyses may not be appropriate if this is a feasibility or pilot study, but end-point analysis plans are always appropriate even if only exploratory. Provide all information requested below, or provide justification if not including all of the information.

Power Statement: Previous studies have found a clear benefit between AP and standard using 16 patients per group, so the sample size of 40 patients for data collection and comparator should be sufficient.

Data Analysis Plan: Data from the 5 sites will be de-identified and collected at each site. CGM data will be compared to time-matched SMBG data to confirm accuracy in the pregnant population. Patterns of insulin and glucose control change will be analyzed and association with outcomes calculated. This data will also be used as a comparator for AP studies as a historical or active control group.

Endpoints

Primary:

Time in range defined as 63-140 mg/dL as determined by CGM analysis

Secondary:

Glycemic Outcomes:

- Frequency of hypoglycemia defined as <63 mg/dL and percent of time in the hypoglycemic range
- Frequency and duration of severe hypoglycemic events defined as requiring assistance from another, an emergency room visit or treatment with glucagon due to unconsciousness
- Time spent above target range defined as >140 mg/dL
- Episodes of clinically significant hyperglycemia with CGM > 180 mg/dL
- Extent of glucose variability
- Percent of time CGM active
- Concordance of CGM data in relation to SMBG data

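### The planned sample size contradicts itself: 300 in total with 60 at Mayo, 10 at Mayo, or 40 overall, with 3 or 5 sites

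*Combined protocol and SAP*

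**What the plan says.** All of the following is current text in one protocol version (V3).

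- **Subject Information, Target accrual:** "Target accrual: 300 subjects across 3-5 sites. We plan to enroll 60 patients each at Mount Sinai New York, Mayo Clinic Rochester". The sentence goes on to name Sansum as the third site at 60. The next one says "In addition, we hope to extend the study to sites such as the Barbara Davis Center" and also mentions the Joslin Clinic. It gives no number for either extra site.
- **Resources (1a):** "Mayo Clinic staff will perform the activities described above for 10 participants". The other sites are to do the same for their own participants.
- **Data Analysis, Power Statement:** because earlier studies with 16 patients per group found a benefit of the artificial pancreas (AP) over standard care, "the sample size of 40 patients for data collection and comparator should be sufficient".
- **Site count:** Methods has "All pregnant women with T1D at up to five sites on insulin pumps". The data analysis text under Study Design and Methods has "Data from the 3 sites will be de-identified and collected in a central HIPPA compliant data repository". The Data Analysis Plan has "Data from the 5 sites will be de-identified and collected at each site".
- **Use of the data beyond the AP comparison:** the Data Analysis Plan says "Patterns of insulin and glucose control change will be analyzed and association with outcomes calculated". The earlier data analysis text lists the maternal and fetal outcomes, among them malformations, preeclampsia and shoulder dystocia.

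**The concern.** Three sections give three sizes, and none refers to the others. The planned N sets the precision of the primary time-in-range estimate. It also decides which associations with maternal and fetal outcomes the cohort could show. The one justification in the document is for 40 and concerns only AP against standard care. No N is justified for the association analyses, whose sensitivity at 40 is very different from that at 300. A reader cannot tell what size the study is meant to reach, cannot later judge whether it got there, and cannot tell whether the Mayo site is resourced for 10 women or 60.

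**Working it through.** **1. Reproduce the stated total.** Inputs from Target accrual: 60 per named site and 3 to 5 sites.

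| Sites | × 60 per site | × 10 per site |
|---|---|---|
| 3 | 180 | 30 |
| 4 | 240 | 40 |
| 5 | 300 | 50 |

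The 300 reproduces exactly as 5 × 60. This assumes that both hoped-for sites open and that each enrols 60, which the protocol does not say. The three named sites give 180.

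**2. Look for a reading that reconciles the figures.**
- Mayo at 60 already exceeds a study total of 40.
- Mayo at 10 fits a total of 40 if four sites enrol 10 each. Four lies within the 3–5 range but is not stated as the site count, and this reading contradicts both 60 per site and 300.
- The Power Statement attaches 40 to data collection as well as to the comparator role, so the text does not limit 40 to the AP comparison.

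**3. Size of the conflict.** Totals: 300/40 = 7.5. Mayo: 60/10 = 6.

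**4. Precision of mean time in range.** The 95% half-width is 1.96 × SD/√N. The ratio between N = 40 and N = 300 is √(300/40) = 2.74 for any common SD. The documents give no between-patient SD, so 10 and 15 percentage points are assumed.

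| N | SD 10 | SD 15 |
|---|---|---|
| 40 | ±3.10 | ±4.65 |
| 180 | ±1.46 | ±2.19 |
| 300 | ±1.13 | ±1.70 |

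The Background offers a rough check on the SD. The overnight crossover study of 16 women reports a 95% CI of 6.1 to 24.2 points for the difference in time in range.
- Half-width: (24.2 − 6.1)/2 = 9.05.
- Standard error: 9.05/2.131 (t, 15 df) = 4.25.
- SD of the paired difference: 4.25 × √16 ≈ 17.
- Per-period SD, 17/√(2(1 − ρ)): about 12 if the within-patient correlation ρ is 0, and about 17 if it is 0.5.

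So 15 may be too low as an upper value. At SD 17 the half-widths are 1.96 × 17/√40 = 5.3, 1.96 × 17/√180 = 2.5 and 1.96 × 17/√300 = 1.9. These are overnight data and only a guide.

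**5. Sensitivity of an association analysis.** The smallest correlation detectable with 80% power at two-sided 5% is tanh((1.96 + 0.842)/√(N − 3)).
- N = 40: tanh(2.802/√37) = 0.43
- N = 180: tanh(2.802/√177) = 0.21
- N = 300: tanh(2.802/√297) = 0.16

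For a binary outcome with an assumed frequency of 10% to 20%, the expected events are 4–8, 18–36 and 30–60 respectively.

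**6. Accrual, for context only.** From the pump-user counts in Preliminary Data, and assuming that every one enrols:
- Mayo: 32 over 4 to 5 years is 6.4–8.0 a year, so 60 takes 7.5–9.4 years.
- Mount Sinai: 48 over 5 to 6 years is 8.0–9.6 a year, so 60 takes 6.25–7.5 years.
- Sansum: 10 a year, so 60 takes 6 years.

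The Mayo counts date from 2009–2013 and volumes may have changed. This does not prove 60 per site unattainable.

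**The case against.** Several points on the other side are fair.

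- **300 is not an arithmetic error.** It equals 5 × 60, and the protocol openly says that two sites are only hoped for. This stands. The fault is that 300 is not labelled as depending on five sites.
- **The site-count conflict is narrow.** The 3–5 range in Target accrual and the limit of five in Methods agree. Only the definite 3 and the definite 5 in the two analysis sections clash, in sentences about where data are de-identified and collected. This stands, and it makes the site count the lesser part of the problem.
- **40 may be a statement of adequacy.** A larger target would also satisfy it. But the Power Statement calls 40 the sample size for both of the cohort's functions, and nothing marks it as a floor. Nor would this reading explain 60 against 10 at Mayo.
- **The template defines target accrual as the Mayo number.** The entry itself spreads 300 over several sites and gives Mayo 60, so the definition does not help.
- **The association analyses are loosely specified.** Maternal and fetal outcomes are not among the listed endpoints, and no test or error rate is given for them. The detectable correlations are therefore a yardstick and do not describe a planned test. Even so, both analysis sections commit to calculating associations with outcomes.
- **This is a minimal-risk observational cohort, with no stopping rule or error-rate claim tied to N.** That limits the harm. However, the template's allowance is for feasibility or pilot studies. This protocol does not call itself either, and it supplies a Power Statement that disagrees with its own target.

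**Conclusion.** The contradiction is real and needs correcting before anyone relies on the stated size. The current text supports a total of 300 or 40 (7.5-fold) and a Mayo contribution of 60 or 10 (6-fold). Only 180 is backed by named sites at the stated 60 each. These figures, and the 2.7-fold ratio of confidence interval widths, need no assumed SD or event rate. The absolute half-widths (±3.1 to ±4.6 points at 40 against ±1.1 to ±1.7 at 300) rest on an assumed SD of 10 to 15, and they widen if the SD is nearer 17. The event counts rest on assumed frequencies of 10% to 20%. The documents do not show which N is intended.

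**What to change.** The sponsor should choose one planned total, one site count and a per-site split that sums to the total. These should appear identically in Target accrual, Resources (1a), the Power Statement and both data analysis sections.

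- If 300 is a ceiling or depends on five sites joining, say so and give the number expected from the three committed sites.
- If 40 is only the minimum for the AP comparison, say so. Then state the N on which the maternal and fetal association analyses rest, with the precision expected at that N.

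The cost is wording plus a short precision statement. The headline accrual or the stated precision may look less favourable afterwards.

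### The protocol gives two incompatible totals (40 and 300) and two incompatible Mayo Clinic numbers (10 and 60), and the only rationale for 40 leaves its adequacy undetermined

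*Combined protocol and SAP*

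**What the plan says.** **Total.** The Power Statement under Data Analysis concludes: "so the sample size of 40 patients for data collection and comparator should be sufficient". Subject Information sets a different figure: "Target accrual: 300 subjects across 3-5 sites". The only ground offered for the smaller number is this: "Previous studies have found a clear benefit between AP and standard using 16 patients per group".

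**Mayo Clinic.** Resources: "Mayo Clinic staff will perform the activities described above for 10 participants". Subject Information: "We plan to enroll 60 patients each at Mount Sinai New York, Mayo Clinic Rochester", with Sansum as the third named site. For the rest, "we hope to extend the study to sites such as the Barbara Davis Center" and the Joslin Clinic; no enrolment number is given for these.

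**Sites.** The data analysis paragraph under Study Design and Methods: "Data from the 3 sites will be de-identified and collected in a central HIPPA compliant data repository". The Data Analysis Plan: "Data from the 5 sites will be de-identified and collected at each site". The Methods allow up to five sites.

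**Role and endpoint.** The Aims make service as a comparator for AP-treated women the overall goal. The Data Analysis Plan foresees use as either a historical or a concurrent control. The primary endpoint is CGM time in range, 63-140 mg/dL, not limited to the night. The Hypothesis names both time in range and hypoglycaemia below 63 mg/dL.

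**The concern.** A sample size is a figure that sites, the ethics board and later AP protocols rely on. Here a reader cannot tell whether the plan is for 40 women or 300, or whether Mayo Clinic is to enrol 10 or 60.

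The Power Statement is also the only argument for any size. It claims sufficiency without saying for which endpoint, what difference or what AP-group size. It appears to borrow from crossover studies, in which each woman is compared with herself, to support a cohort that will be compared with different women.

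**Working it through.** **1. Totals.** 300 / 40 = 7.5. The Power Statement applies 40 to data collection as well as to the comparator role, so it covers the whole study. It does not call 40 a minimum or an interim figure.

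**2. Mayo Clinic.** 60 / 10 = 6.

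**3. Can the site count explain the gaps?** At 10 per site, three, four or five sites give 30, 40 or 50. At 60 per site they give 180, 240 or 300. So 40 would match four sites at 10 each, but the protocol never says this. No site count from 3 to 5 turns one total into the other.

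**4. Can 40 be reproduced?** No. The Power Statement gives no endpoint, target difference, SD, alpha, power, AP-group size or dropout rate.

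**5. The apparent source.** The Power Statement cites no reference, so the link is an inference. The only 16-subject AP studies described (Background) are two randomised crossovers, 16 women in each, every woman her own control.

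| Result as reported | Overnight study | Day-and-night study |
|---|---|---|
| Overall time in range | not reported | comparable, no figures |
| Overnight time in range | 74.7 vs 59.5%, 95% CI 6.1 to 24.2, P = 0.002 | 67.7 vs 60.6%, P = 0.06 |
| Hypoglycaemia | no figures | fewer episodes, P = 0.04; time <63 mg/dL 1.6 vs 2.7%, P = 0.02 |

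The benefit is therefore real but falls on a different endpoint in each study. Neither study is reported as showing a gain in overall time in range.

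**6. Loss of pairing.** With SD σ and within-woman correlation ρ, the variance of the mean difference is 2σ²(1−ρ)/16 in the crossover and 2σ²/n for two separate groups of n. These are equal when n = 16/(1−ρ). The documents do not give ρ. For assumed ρ:

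- ρ = 0: n = 16
- ρ = 0.3: n = 22.9, so 23
- ρ = 0.5: n = 32
- ρ = 0.7: n = 53.3, so 54

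Forty per group matches the crossover precision up to ρ = 1 − 16/40 = 0.6. This assumes an AP group of the same size and equal SDs, and makes no allowance for confounding. So 16 does not transfer as it stands, but 40 may or may not be enough to make up for the lost pairing.

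**7. What each size delivers by itself.** The documents give no SD for time in range, so a range is assumed, guided by the crossovers under a paired t analysis.

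- Overnight study: SE = (24.2 − 6.1)/2 / 2.131 = 9.05/2.131 = 4.25; paired SD = 4.25 × √16 = 17.0. Its P value gives 15.2/3.733 × 4 = 16.3.
- Day-and-night study: P = 0.06 gives t(15) = 2.034; SE = 7.1/2.034 = 3.49; paired SD = 3.49 × 4 = 14.0.
- Between-woman SD = paired SD / √(2(1−ρ)). For ρ from 0 to 0.7 this is 12.0 to 21.9 (overnight study) and 9.9 to 18.0 (day-and-night study), so roughly 10 to 22 points. Both are overnight figures.

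Half-width of the 95% CI = t(0.975, n−1) × SD / √n:

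| Assumed SD (points) | n = 40 | n = 300 |
|---|---|---|
| 10 | 3.2 | 1.1 |
| 12 | 3.8 | 1.4 |
| 17 | 5.4 | 1.9 |
| 22 | 7.0 | 2.5 |

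**The case against.** **Site count.** A reader might infer that 3 sites in one paragraph and 5 in another is a contradiction. The Methods and Subject Information set out a deliberate range, and the two paragraphs quote its ends. Only loose wording remains.

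**180, or 300 only at five sites of 60.** A reader might treat 180 as a third planned total, or say that 300 needs 60 women at all five sites. The protocol gives 60 for the three named sites and no number for the others, so 180 is only a product and the other 120 could be split in any way. The stated totals are two: 40 and 300.

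**Misquotation.** It is tempting to say that the Power Statement misreports its source. It names none. In a crossover each condition does have 16 women, and the Background itself speaks of groups when describing one. The phrase may be loose usage. What stands is that those studies had 16 women in total and were paired, and this cohort is not.

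**No power needed.** The template lets feasibility and pilot studies omit a power analysis, this is a minimal-risk observational cohort, and the AP comparison belongs to other protocols. That limits the seriousness. But the protocol claims no such exemption and does assert sufficiency.

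**Innocent readings of the sizes.** The template defines target accrual as the Mayo Clinic number, but the entry itself spreads 300 across sites. Reading 40 as a minimum is not supported by the text and leaves 10 against 60 unexplained. This part of the defence does not stand.

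**Conclusion.** The size contradictions hold on the face of the current text: 40 against 300 in total (7.5-fold) and 10 against 60 at Mayo Clinic (6-fold). They rest on no assumption.

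The rationale for 40 does not support it as written. It has no inputs, its evident basis is paired data on 16 women per study, and only one of those studies showed a clear time-in-range gain, overnight. That second part rests on inferring the source.

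A reader might go on to conclude that 40 is too small. The documents do not support that: the answer depends on the effect, the within-woman correlation and the AP-group size, none of which is stated. A power table could be built, but it would rest on assumed inputs and the conclusion does not need it. The right word is undetermined. The point should be fixed, but it is not a reason to doubt the design of an observational cohort.

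**What to change.** 1. Reconcile 40 with 300, and 10 with 60. State one planned total and one Mayo Clinic number. Align the two data-handling paragraphs with the 3-5 site range.
2. In the Power Statement, replace the 16-per-group phrase and the unqualified benefit claim with an accurate account: two crossovers of 16 women each; a clear overnight time-in-range gain in one; comparable overall time in range with less hypoglycaemia in the other.
3. Replace the sufficiency claim with the 95% CI half-width for mean time in range at the reconciled size, labelling the SD as an assumption. Leave the power of the AP comparison to the AP protocols.

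The cost is protocol wording and one decision on size. The stated justification becomes less favourable. The correction itself requires no extra patients.
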